## 5. STUDY SETTING

This is a single centre study. The study population will include women diagnosed with breast cancer undergoing surgical treatment with breast conserving surgery (BCS) in the Breast Unit of University Hospitals of Derby and Burton NHS Foundation Trust.

## 6. ELIGIBILITY CRITERIA

### 6.1. Inclusion Criteria

- Women with breast cancer diagnosis (both invasive and in-situ) undergoing BCS with or without oncoplastic techniques.

### 6.2. Exclusion Criteria

- Excision of skin and/or nipple-areola complex required.

## 7. STUDY PROCEDURES

### 7.1. Recruitment

#### 7.1.1. Patient Identification

- Suitable patients will be identified during the routine multi-disciplinary meetings.
- All suitable patients identified following pre-operative MDT discussion will be automatically eligible if they opt for BCS.

#### 7.1.2. Screening

Not applicable.

#### 7.2. Consent

Informed consent is not required for this study, as it does not involve any deviation from standard patient care. This study does not involve sharing any identifiable patient information outside of the treating team. Only anonymous data will be used to carry out the research. The data obtained by reviewing routinely collected patient information and tests for the purpose of this study will not have any impact in patients' diagnosis and treatment.

#### 7.3. Study Assessments

Participants will undergo ALL treatments as per standard local practice.

Breast conserving surgery will be performed as per standard local practice.

In the surgical theatre, following the WLE, the surgical specimen will be processed as per standard practice. This involves:

- Specimen x-ray
- Measurement of specimen weight

The specimen is subsequently sent (either fresh or in formalin) to the Pathology department for processing. There, in addition to the routine procedures, the specimen volume will be measured by water displacement using the following procedure (same for Phase 1 and Phase 2):

- The WLE specimen is placed into a graduated jug of known capacity which is subsequently filled completely with water.
- The specimen is removed, and the water is transferred into a class A measuring cylinder to measure the volume.
- The WLE specimen volume will be obtained by subtracting the measured water volume from the maximum capacity of the graduated jug.

The histology specimens will be examined and reported according to standard local practice. Additionally, the specimen volume will also be added to the report.

Full schedule of assessments is shown in Appendix 1.

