#### 3.2. Outcomes

**Phase 1 primary outcome:** A regression model using a combination of variables from specimen weight, radiological density, patient's age, patient's BMI, tumour histology and grade that predicts surgical specimen volume as accurately as possible.

**Phase 1 secondary outcomes:** not applicable.

**Phase 2 primary outcome:** The 95% limits of agreement (Bland and Altman [15]) with 95% confidence limits of the novel method using the regression model and the current method (dividing the specimen weights by 0.958, regardless of their radiological density) against the gold standard measurement of specimen volume (the water displacement / Archimedes method).

**Phase 2 secondary outcome 1:** The Intraclass correlation (ICC) of the estimates using the new method and the current method. This will indicate how strongly the two methods resemble each other.

**Phase 2 secondary outcome 2:** A within-patient comparison of the new method and the current method using a paired t-test.

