#### **10.3.2. Outcome Analysis**

Study phase 1 primary outcome: A regression model to estimate the tissue volumes.

This phase will include the 6 explanatory / independent variables:

1. The diameter of the mass (mm)
2. The healthy tissue density (using a Visual Analogue Scale (VAS))
3. The area occupied by the tumour (% of tissue sample)
4. Specimen weight (g)
5. Patient age
6. Patient BMI

The outcome / dependent variable will be the tissue volume, measured using the water displacement / Archimedes principle.

The regression model will be fitted using a bi-directional stepwise regression. Variables will be included if they make an important improvement in the model's fit. They will be excluded if, after other variables have been included in the model, they no longer make an important improvement in the model's fit. The model will stop fitting variables when both of the following conditions are met:

1. None of the variables that are not already included will make an important difference to the model's fit if they are included.
2. All of the variables that are included do make an important difference, so none of them should be removed.

The definition of "important" improvements in the model's fit and how they will be assessed will be described in detail in the Statistical Analysis Plan.

Study phase 2: Assessing the accuracy of the model obtained from phase 1.

This phase of the study will use a second collection of tissue samples, that have not been used to develop the model. It is needed because the regression model has been developed to predict the tissue volumes of the first sample as accurately as possible. It may not estimate other patients' volumes as accurately as these patients and we need to demonstrate that, even if the estimates for

other patients are less accurate than for the original sample of patients, they are still more accurate than the current method.

Study phase 2 primary outcome: Comparison of the new regression-based method and the current method with the gold standard measurement (using the Archimedes/water-based method). The estimates will be compared to the measured tissue volumes using two limits of agreement analyses (Bland and Altman [15]).

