Study phase 2 secondary outcome 1: The differences between the two estimation methods and the gold standard tissue volumes will be compared using intraclass correlation. This will demonstrate how strongly related the two estimation methods are to each other. This is not a within-patient comparison but a comparison closely the results from the new estimation methods resemble the results from the current method.

Study phase 2 secondary outcome 2: The differences between the two estimation methods and the gold standard will be compared within-patient using a paired t-test. The mean difference in accuracy and its standard deviation will be reported.

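### The reference volume in section 7.3 counts retained water as tissue; a systematic error of this kind is absorbed by the fitted equation but shifts the mean difference of the uncalibrated current method

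*Protocol*

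**What the plan says.** Protocol section 7.3 gives the measuring procedure, which is the same in both phases. First, "The WLE specimen is placed into a graduated jug of known capacity which is subsequently filled completely with water". Then "The specimen is removed, and the water is transferred into a class A measuring cylinder to measure the volume". Finally, "The WLE specimen volume will be obtained by subtracting the measured water volume from the maximum capacity of the graduated jug". The section does not say how the capacity is known. It mentions no draining of the specimen, rinsing of the jug, blank run or allowance for water that does not reach the cylinder.

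Section 10.3.2 makes this reading the regression target: "The outcome / dependent variable will be the tissue volume, measured using the water displacement / Archimedes principle". The comparator, in section 3.2, is a fixed rule: "dividing the specimen weights by 0.958, regardless of their radiological density". Both are judged against the same reading in Phase 2: "The estimates will be compared to the measured tissue volumes using two limits of agreement analyses". For the second secondary outcome, "The differences between the two estimation methods and the gold standard will be compared within-patient using a paired t-test". The study summary states the aim as showing that the new method is superior to the current one.

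**The concern.** The reference does two jobs. It calibrates the new method in Phase 1 and judges both methods in Phase 2. If it carries a systematic error, the fitted equation learns that error, while a divisor fixed in advance cannot. Testing on fresh Phase 2 specimens protects against overfitting but not against a measurement error common to both phases.

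What is at stake is the interpretation of a difference in mean bias. Part of it could come from the new method having been tuned to the measuring procedure rather than from any information in radiological density, and the planned analyses described in the protocol would not separate the two.

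**Working it through.** **The plan's own figure.** Section 10.1 gives 246 specimens from SD 23.26% and a 5% half-width for the confidence limits of the limits of agreement. With half-width = t(0.975, n−1) × SD × √(1/n + 1.96²/(2(n−1))), n = 246 gives 4.999%, and it is the smallest n at or below 5%. The stated size is reproduced, and this point does not change it.

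**Mass balance.** Let C be the stated capacity, F the volume to which the jug is actually filled, V the true specimen volume and r the water retained on the specimen or in the jug.

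- Water reaching the cylinder = F − V − r.
- Recorded volume = C − (F − V − r) = V + r + (C − F).
- If F = C, the recorded volume is V + r. Since r cannot be negative, this part of the error is upward.
- The term C − F can take either sign. If the jug is filled above the level that C refers to, it is negative and offsets r.

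The accuracy of a class A cylinder does not help, because the retained water never reaches it.

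**Passage into the comparison.** Write the mean systematic error as δ. A regression with an intercept, fitted to V + δ, predicts V + δ. Its mean difference from the Phase 2 reference is then about zero. The current method's difference is weight/0.958 − V − δ, so its mean moves by −δ. If δ is constant in millilitres, the SD of the millilitre differences, and hence the width of the limits, is unchanged. Specimen-to-specimen variation in r widens both methods' limits.

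A simulation illustrates this (1,500 runs, 110 fitting and 246 validation specimens, weight-only linear model with intercept, weight/0.958 unbiased for true volume, median volume 50 ml). With mean r of 0, 2 and 5 ml, the fitted intercept was 0.09, 2.09 and 5.09 ml. The mean difference was about 0 for the new method throughout, and 0, −2.0 and −5.0 ml for the current one. At r = 2 ml the SDs of the differences were almost equal (1.72 and 1.70 ml).

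**Size.** Neither r nor V is in the protocol, so both are assumptions. Excess = r/V:

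| V (ml) | r = 1 ml | r = 2 ml | r = 5 ml | r that gives 5% |
|---|---|---|---|---|
| 30 | 3.3% | 6.7% | 16.7% | 1.5 ml |
| 50 | 2.0% | 4.0% | 10.0% | 2.5 ml |
| 100 | 1.0% | 2.0% | 5.0% | 5.0 ml |
| 150 | 0.7% | 1.3% | 3.3% | 7.5 ml |

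**Would it be visible?** The 95% confidence half-width of the mean difference is 1.96 × 23.26/√246 = 2.9%. A shift above that size would be distinguishable from zero in Phase 2. The limits themselves lie about 1.96 × 23.26 = 45.6% either side of the mean.

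**The case against.** Several objections have force.

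- **Capacity.** A reader might infer that the protocol subtracts a nominal, uncalibrated capacity. It does not say so: the text calls the capacity known and maximum, and a calibrated value fits that wording. If the capacity had been found by the same fill-and-pour route, jug residue would cancel. Water carried out on the specimen would not.
- **Direction.** A reader might infer that the reference is always too high. Only the retained-water part is one-way; the sign of the total error cannot be derived from the text. Nor does the shift always count against the current method. Where weight/0.958 overestimates true volume, an upward reference error would hide part of that.
- **Consequence.** A reader might infer that this error would decide which method is more accurate. Against an SD of 23.26%, a 4% shift raises root-mean-square error only to √(23.26² + 4²) = 23.6%. In the simulation at r = 2 ml the ranking by root-mean-square error did reverse: new against current was 1.73 against 2.63 ml judged by the reference, but 2.38 against 1.28 ml judged by true volume. That rests on far less noise than the audit SD suggests, so it shows that reversal is possible, not that it is likely.
- **Benchmark.** A reader might set 2 ml on 50 ml (4%) against a largest possible density effect of about 4%, since 0.92/0.958 − 1 = −4.0% and 1.00/0.958 − 1 = +4.4%. Those bounds cover fat and fibro-glandular tissue only. Section 1 says tumour is denser, and section 4 puts it at 2% to 30% of the excised tissue, so the protocol does not cap the effect there.
- **Place.** Drain times often sit in laboratory instructions, and an extra comparison may be in the statistical analysis plan, which is not shown.

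What stands is that section 7.3 itself fixes a subtraction that counts retained water as tissue, and nothing in the protocol offsets the unequal effect on the two methods.

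**Conclusion.** The point holds in a limited form. By the stated subtraction, retained water is recorded as tissue, with a fill-level or capacity error adding to or offsetting it. Any systematic net error is absorbed by the regression and moves the mean difference of the current method only. It shifts the centre of that method's limits of agreement, not their width; this is exact for a constant error in millilitres and approximate on a percentage scale, where a fixed amount weighs more in small specimens.

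The size rests wholly on assumed values: 0.7% to 16.7% for 1 to 5 ml on 30 to 150 ml. It is slight for large specimens. For small ones it can exceed both the 2.9% confidence half-width and the 5% difference that section 10.1 regards as able to affect boost accuracy. The protocol does not support a claim that the net error must be upward, or that it would determine which method wins. It is a cheap improvement to a comparison that can be biased if section 7.3 is followed as written.

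**What to change.** **Section 7.3.** Set each jug's effective capacity by blank runs: fill to the same level without a specimen, pour, and read in the same cylinder. Subtract the poured water from that value. This corrects jug residue and fill level only; the remaining error is the water carried out on the tissue. To limit that, drain the specimen over the jug for a fixed time before pouring.

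**Section 10.3.2.** Add a comparison in which the current method uses a single constant density re-estimated from Phase 1. A weight-only linear calibration with an intercept is preferable, because a single constant does not fully absorb a fixed offset in millilitres. The gain of the full model over this comparator is then due to the added variables, radiological density among them, rather than to recalibration to the reference. If the statistical analysis plan already contains this comparison, a cross-reference is enough.

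**Cost.** A one-off calibration of each jug, a short drain step per specimen and one extra analysis. The sample size does not change.

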#### 7.4. Withdrawal Criteria

Not applicable.

## 7.5. Storage and Analysis of Samples

Surgical specimens will be processed immediately in pathology as per standard practice and the volume will be measured and recorded at that point. There will be no storage of material for research purposes.

## 7.6. End of Study

The end of study will be defined as the last data capture for the last participant. The Clinical Trials Manager will notify the Sponsor, participating sites and REC within 90 days of the end of study. The clinical study report will be written within 12 months of the end of study.

## 8. SAFETY REPORTING

### 8.1. Definitions

Term	Definition
Adverse Event (AE)	Any untoward medical occurrence in a participant, including occurrences which are not necessarily caused by or related to study procedures.
Related AE	An untoward and unintended response in a participant to a study procedure. This means that a causal relationship between the study procedure and an AE is at least a reasonable possibility, i.e. the relationship cannot be ruled out.
Serious Adverse Event (SAE)	
A serious adverse event is any untoward medical occurrence that:
 
 
• results in death
 
• is life-threatening
 
• requires inpatient hospitalisation or prolongation of existing hospitalisation
 
• results in persistent or significant disability/incapacity
 
• consists of a congenital anomaly or birth defect
 
 
Other 'important medical events' may also be considered serious if they jeopardise the participant or require an intervention to prevent one of the above consequences.
 
NOTE: The term "life-threatening" in the definition of "serious" refers to an event in which the participant was at risk of death at the time of the event; it does not refer to an event which hypothetically might have caused death if it were more severe.

Related SAE	An adverse event that is both serious and, in the opinion of the reporting Investigator, believed with reasonable probability to be due to one of the study procedures.
Related & Unexpected SAE	
A serious adverse event that;
 
 
• is believed with reasonable probability to be due to one of the study procedures.
 
• the nature and severity of which is not consistent with the
 

	information provided in the protocol i.e. it is not listed as an expected occurrence.
--	---

## 8.2. Operational Definitions for (S)AEs

All participants in the study will receive standard NHS treatment. This protocol does not contain investigational agent(s). Therefore, events related to the natural course of the disease and its treatment are not required to be reported.

For the purposes of this study, the following events do not constitute SAEs:

- Hospitalisation for:
  - Surgical complications related to breast conserving surgery
  - Pre-planned elective procedures unless the condition worsens
  - Treatment for progression of the patient's cancer
- Progression or death as a result of the patient's cancer

## 8.3. Recording and Reporting SAEs

Collection of AEs is not required for trial analysis.

Whilst it is not anticipated there will be any serious adverse events directly related to the study, it is important that this protocol includes a process for dealing with any unexpected serious adverse events in the unlikely event they occur.

For the purpose of this study, the following are regarded as expected SAEs and should not be reported on an SAE form:

- Haematoma, wound infection, seroma or other complication of breast surgery.

Events that meet the criteria for a SAE, per protocol, must be recorded by the investigator using the 'non-CTIMP safety report to REC form' from the HRA website. The completed form should be submitted to the Sponsor and REC within 15 days of the CI becoming aware of the event.

UHDB contact information:
Email: [contact]

### 8.3.1. Assessment of SAEs

#### 8.3.1.1 Severity

The investigator should determine the severity of the SAE;

- Mild: no interference with daily activities.
- Moderate: moderate interference with daily activities.
- Severe: considerable interference with daily activities (e.g. inability to work).

**NOTE:** to avoid confusion or misunderstanding the term "severe" is used to describe the intensity of the event, which may be of relatively minor medical significance, and is NOT the same as "serious" which is described in the safety definitions.

### **8.3.1.2 Causality**

Clinical judgement should be used to determine the relationship between the study procedures and the occurrence of each SAE;

- Not-related: There is no evidence of a causal relationship between the event and study procedures.
- Related: There is evidence of a causal relationship between the event and study procedures i.e. a relationship to the study procedures cannot be completely ruled out.

Assessment of causality must be made by a medically qualified doctor (usually the principal investigator).

### **8.3.1.3 Expectedness**

The assessment of expectedness is only required if the event is deemed to be related to study procedures.

- Expected: Event previously identified and described in the protocol.
- Unexpected: Event not previously described in the protocol.

The expectedness assessment is delegated to CI.

## **8.4. Pregnancy reporting**

Not required.

## **8.5. Reporting Urgent Safety Measures**

If any urgent safety measure is taken the research team should inform the Sponsor within 24 hours using the Sponsors safety incident reporting form. The Sponsor will inform the REC and participating sites of the measures taken and the circumstances giving rise to those measures within 3 days on implementation of the urgent safety measure.

## **9. DATA HANDLING**

### **9.1 System and Compliance**

Study data will be entered at site into paper case report forms (CRF) directly or onto worksheets by study personnel. The worksheet data must be transferred into the CRF within 5 days of data collection. Participants will be identified only by their unique study number. The NHS numbers will be linked to the study numbers and this information will be stored securely locally with restricted access only to investigators who are part of the patients' treating team. Only the study number will be entered in the study database. The database will consist of a password protected Excel spreadsheet.

Processing of study data and checking for consistency, validity and quality will be undertaken by study statisticians at Derby Clinical Trials Unit prior to analysis. Data checks will include out-of-range data, cross-checks for conflicting data, missing data and data queries.

## 9.2 Source Data

Source documents are where data are first recorded, and from which participants' CRF data are obtained. These include, but are not limited to, hospital records (from which medical history and previous and concomitant medication may be summarised into the CRF), clinical and office charts, laboratory and pharmacy records, diaries, microfiches, radiographs, and correspondence.

CRF entries will be considered source data if the CRF is the site of the original recording (e.g. there is no other written or electronic record of data). All documents will be stored safely in confidential conditions. On all trial-specific documents, the participant will be referred to by the trial participant number, not by name.

Investigators should keep records of all participating patients and copies of any worksheets. It is necessary for investigators to provide access to source document for monitoring and audit purposes to Sponsor, any monitoring or regulatory authorities as deemed necessary.

Study variable	Source data
Measured tissue sample volumes	Histopathology report
Measured specimen weight	Histopathology report
Radiological density of healthy breast tissue on specimen x-ray	CRF
Tumour diameter on specimen x-ray	CRF
Percentage of specimen occupied by tumour	CRF
Tumour histology	Histopathology report
Tumour grade	Histopathology report
Patient age	Hospital records
Patient BMI	Hospital records

## 9.3 Workflow

Data will be collected and retained in accordance with the Caldicott Principles, UK Data Protection Act 2018 and General Data Protection Regulation (GDPR).

## 9.4 Data Access and Security

Direct access will be granted to authorised representatives from the Sponsor, host institution and the regulatory authorities to permit study-related monitoring, audits and inspections.

## 9.5 Archiving

At the end of the study, following completion of the end of study report, UHDB will securely archive all centrally held study related documentation for a minimum of 5 years. At the end of the defined archive period arrangements for confidential destruction will be made. It is the responsibility of the PI to ensure that data and all essential documents relating to the study are retained securely for a minimum of 5 years after the end of study, and in accordance with national legislation. All archived documents must continue to be available for inspection by appropriate authorities upon request.

